# Appendix V - FACT-G Quality of Life Questionnaire

## FACT-G (Version 4)

Below is a list of statements that other people with your illness have said are important. Please circle or mark one number per line to indicate your response as it applies to the past 7 days.

	PHYSICAL WELL-BEING	Not at all	A little bit	Some- what	Quite a bit	Very much
GP1	I have a lack of energy	0	1	2	3	4
GP2	I have nausea	0	1	2	3	4
GP3	Because of my physical condition, I have trouble meeting the needs of my family	0	1	2	3	4
GP4	I have pain	0	1	2	3	4
GP5	I am bothered by side effects of treatment	0	1	2	3	4
GP6	I feel ill	0	1	2	3	4
GP7	I am forced to spend time in bed	0	1	2	3	4
	SOCIAL/FAMILY WELL-BEING	Not at all	A little bit	Some- what	Quite a bit	Very much
GS1	I feel close to my friends	0	1	2	3	4
GS2	I get emotional support from my family	0	1	2	3	4
GS3	I get support from my friends	0	1	2	3	4
GS4	My family has accepted my illness	0	1	2	3	4
GS5	I am satisfied with family communication about my illness	0	1	2	3	4
GS6	I feel close to my partner (or the person who is my main support)	0	1	2	3	4
Q1	Regardless of your current level of sexual activity, please answer the following question. If you prefer not to answer it, please mark this box and go to the next section.					
GS7	I am satisfied with my sex life	0	1	2	3	4

English (Universal)

Copyright 1987, 1997

Enge 1 of 2

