### 4.1 Inclusion Criteria

- **4.1.1** Any histologically or cytologically confirmed advanced/metastatic solid tumor cancer (except pancreatic cancer and primary brain tumor), that has failed at least 2 prior lines of therapy given either in the recurrent or metastatic setting and must be refractory to or intolerant of existing therapy(ies) known to provide clinical benefit for their condition.
- 4.1.2 Measurable disease per RECIST v 1.1. A single target lesion is considered measurable disease provided the lesion meets the definition of measurability as described in RECIST 1.1 (Schwartz 2016). If a target lesion has been surgically removed or treated with radiotherapy, it is not evaluable for response. Although not a requirement for eligibility, patients with tumor assessable may be asked if willing to undergo an optional research related biopsy prior to treatment start and prior to the 3rd treatment course interested participants would provide consent through a separate optional biopsy consent form. Note: If a biopsy is obtained prior to treatment start (any time after consent) and a patient is later deemed ineligible to receive treatment, the tumor sample will not be used for research purposes.
- **4.1.3** Resolved acute effects of any prior therapy to baseline or Grade ≤1 NCI CTCAE v5 except for AEs not constituting a safety risk in the opinion of the enrolling Investigator.
- **4.1.4** Age 18 years or older at the time of consent.
- **4.1.5** ECOG Performance Status 0 or 1. (Refer to Appendix I).
- **4.1.6** Evidence of adequate organ function within 14 days prior to treatment on Cycle 1 Day 1 defined as:
  - hemoglobin ≥9 g/dL (may be transfused not more than 2 units of pRBCs within previous 2 week to meet this requirement)
  - absolute neutrophil count (ANC) ≥1500/ul
  - platelets ≥100 x 10^9/L (may be transfused not more than 1 unit of platelets within previous 2 week to meet this requirement)
  - estimated glomerular filtration rate (eGFR) >40 mL/min or creatinine: ≤1.5 x upper limit of institutional normal (ULN)
  - ALT. AST and ALP ≤ 2.5 x ULN or ≤ 5 x ULN if liver metastases

- **4.1.7** Adequate pulmonary function with PFTs >50% FEV1 if symptomatic or known impairment.

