### 4.2 Exclusion Criteria

- **4.2.1** Pregnant or breastfeeding. Persons of child-bearing potential must have a negative pregnancy test (serum or urine) within 14 days of treatment start.
- **4.2.2** History of clinically significant vascular disease, including any of the following within 6 months prior to start of study treatment: MI or unstable angina, percutaneous coronary intervention, bypass grafting, ventricular arrhythmia requiring medication, stroke or transient ischemic attack, symptomatic peripheral arterial disease.
- 4.2.3 Marked baseline prolongation of QT/QTc interval (e.g., demonstration of a QTc interval ≥470 milliseconds by Fridericia correction). If undiagnosed MI(s) appear on ECG, work up as medically warranted and determine eligibility based on findings. Cardiac function should be monitored by clinical examination and assessment of vital signs for hypotension, arrhythmia, angina, and myocardial infarction during the study period per Section 6.1.1.
- **4.2.4** Known or suspected untreated CNS metastases are excluded. Persons are eligible if CNS metastases are treated and they are neurologically stable for at least 2 weeks prior to enrollment. In addition, must be either off

- corticosteroids, or on a stable or decreasing dose of  $\leq$  10 mg daily prednisone (or equivalent).
- **4.2.5** Anti-cancer treatment including surgery, radiotherapy, chemotherapy, other immunotherapy, or investigational therapy within 14 days before treatment start.
- **4.2.6** Prior malignancy except for the following: adequately treated basal cell or squamous cell skin cancer, in situ cervical cancer, adequately treated Stage I or II cancer currently in complete remission, or any other cancer from which the patient has been disease-free for 3 years after surgical treatment.
- **4.2.7** Known hypersensitivity or history of allergic reactions attributed to compounds of similar chemical or biologic composition to the agents used in the study.
- **4.2.8** Prior therapy with TGF-β antagonist, IL-15 or analogs.
- **4.2.9** Ongoing use of St. John's Wort and/or other herbal CYP modulators as certain cytokines, including IL-2 and TGF-β, have been found to suppress the activities of cytochrome P450 enzymes. The participant may be considered for the study if they discontinued the herbal CYP modulator at least 7 days before the 1st dose of HCW9218 and agree not resume it until after the End of Treatment visit.

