#### 8.1 Standard of Care Activities

Standard of care assessments and procedures are part of good clinical care and are charged to the patient and their health insurance.

	Baseline / screening Within 28 days of Cycle 1 Day 1 unless o/w noted¹	Cycle	1					Cycle	2				Cycle 3 and subsequent cycles	Every 4 cycles (12 weeks) or per SOC if more	End of treatment (EOT) visit 3 weeks after the last dose	After EOT visit: Follow-up for response until PD, then survival only every 3 mon
Study day	-28 to -1 (no Day 0)	1	2	3	5	8	15	1	2	5	8	15	1	frequent until PD	of HCW9218	for 12 months from C1D1
window	Not applicable	±1	day us	sing Day	1 as th	ne anch	or	+3 da	ys for I	Day 1	then ±	£1 day	±3 days	± 14 days	± 1 week	± 1 month
Written consent	X1															
Assess for eligibility	Х															
Medical history including prior cancer treatment	Х															
Concomitant medications	X	Х				Χ	Χ	Χ			Χ	Χ	Х		Х	
AE assessment		Χ	Χ	Х	Χ	Χ	Χ	Χ	Χ	Χ	Χ	Χ	Х		Х	
Physical exam 	Х	Χ				Χ		Χ					Х		Х	
Provider assessment	Х	Х			Χ	Χ	Χ	Χ					Х		Х	
ECOG Performance Status	Х	Χ				Χ		Χ							Х	
Vitals signs	Х	X 3	Χ	Х	Χ	Χ	Χ	X 3	Χ	Χ	Χ	Χ	X 		Х	
Weight  plus height at baseline only	X	X 				Χ		Χ				Χ	Х		X	
CBC with differential	X1	X 	Χ	Χ	Χ	Χ	Χ	Χ	Χ	Χ	Χ	Χ	X 		X	
Complete metabolic panel 	X 	X 				Χ		Χ					X 		Х	
CRP, ferritin, amylase, lipase, LDH, mg, phos	X8					X8										
Diagnosis related biomarker (e.g., CA125, PSA)	Х													Х		Х
Pulmonary function testing only if clinically indicated	Х															
Tumor assessment by disease appropriate methods	X 													Х		Х
Disease response based on RECIST 1.1 (until disease progression)	X 													Х		Х
Survival/follow-up																Х

1. Baseline/Screening – within 14 days of study treatment start for labs required for eligibility; prior disease assessments may be used if they were performed within 42 days of the 1st HCW9218 dose in the absence of intervening anti-cancer therapy. Consent is exempt from 28 day limit and may be performed at any time prior to starting study related activities. If more than 14 days pass between lab work for eligibility (found in Section 4.1.6) and Cycle 1 Day 1, the pre Cycle 1 lab results must continue to meet the criteria in Section 4.1.6.

March 29, 2023 Page 41 of 76 confidential

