#### 8.2 Research Related Activities

Activities directly related to participation in the research study are paid for by study funding and not charged to the patient or their health plan/health insurance. Research related activities are linked to a standard of care (SOC) visit and may be adjusted to stay with the SOC visit unless otherwise noted.

Tests and procedures	Baseline/ Screening	Cycle 1						Cycle 2					Cycle 3 and all subsequent cycles	Every 4 Cycles (every 12 weeks)	At End of Treatment (EOT visit)
Study day		1	2	3	5	8	15	1	2	5	8	15	Day 1		
Coagulation studies (INR/PTT) 	Х	Χ	Χ	Χ	Χ	Χ	Χ	Χ	Χ	Χ	Χ	Χ			
ECG and cardiac monitoring 	Χ														
Pregnancy testing (serum or urine) for females of child-bearing potential 	Х	X3													
HCW9218 administration (refer to Section 6.1 for dose adjustment based on weight change)		Х						Х					Х		
Targeted toxicity worksheet ( Appendix IV ) in addition to AE assessment per Section 10.2.2		X 	X 	X 	X 										
Blood sample for pharmacokinetics (PK) 		Pre and post 5	X 5	X 5	X 5	X 5		Pre and post 	X 	X 	X 				Х
Blood sample for correlative marker (CM) analysis 		Pre and post 6	X 	Pre and post8	X8	X8	X8	X8							
Blood sample for immunogenicity (IMG) 		X (prior to dose)						X (prior to dose)					X (prior to dose)		Х
Blood sample for immune cell analysis and TIS biomarkers (p16 and p21) (at least 10 mL collected in Heparin tube)		X (prior to dose)				Χ	Х	x (prior to dose)					X (prior to dose)		
Blood sample for UMN research related testing (at least 30 mL collected in 3 Heparin tubes)		X (prior to dose)	X	X	X	Χ	Χ	x (prior to dose)		Х	Χ	Χ	X (prior to dose)		
FACT-G QOL questionnaire (Appendix V)	X													X	Х
Skin condition questionnaire (Appendix VI)								Х					X		Χ
Tumor biopsy (optional refer to Section 4.1.2)	X10												X (prior to cycle 3 dose only)		

- 1- Coagulation studies are performed in FV labs as usual but charge to research, collect prior to day's dose if applicable
- 2- An ECG as usual will be performed at baseline/screening but charged to research.

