- 10- Patients with accessible tumor and who sign the separate consent for a fresh tumor biopsy collected prior to the 1st HCW9218 dose (any time after consent) and before the 3rd dose of HCW9218. Biopsy collection is exempt from the 28 day limit and may be performed at any time after consent and prior to HCW9218 dose. If a biopsy is obtained prior to the 1st HCW9218 dose and a patient is later deemed ineligible to receive treatment, the tumor sample will not be used for research purposes.

March 29, 2023 Page 44 of 76 confidential

Research related sample collection and activities are linked to a standard of care (SOC) visit and may be adjusted to stay with the SOC visit unless otherwise noted.

Up to 3 additional research samples for each test type may be collected at other time points (i.e., at time of AE, disease progression or response) during the study period.

All research samples go to the Masonic Cancer Center Translational Therapy Lab (TTL) except fresh biopsy or surgical samples are handled as described in the contract with BioNet.

Residual samples (and study data) may be used by HCW Biologics Inc. and shared with University of Minnesota investigators for research studies of additional biomarkers and correlative assessments. Results will not influence a patient's treatment nor will the results be provided to the patient or placed in their medical record.

The following testing is performed at HCW Biologics or their designee lab.

**Pharmacokinetic (PK) analysis** – Detection of HCW9218 levels over time. If appropriate, PK may also be performed using the same samples as immunogenicity and correlative marker analysis.

**Immunogenicity (IMG)** - Detection of Anti-HCW9218 Antibodies will be performed at HCW Biologics Inc.

Correlative Marker (CM) Assessments - These tests will be performed at HCW Biologics as research studies using de-identified samples. Serum samples will be collected to evaluate the levels of serum cytokines, chemokines and inflammatory markers, typically but not limited to TGF- $\beta$  isoforms, IL1 $\alpha$ , IL-1 $\beta$ , IL-6, IFN- $\gamma$ , TNF- $\alpha$ , MCP-1, resistin and CRP.

Residual samples (and study data) may be used by HCW Biologics Inc. and shared with University of Minnesota investigators for research studies of additional biomarkers and correlative assessments. Results will not influence a patient's treatment nor will the results be provided to the patient or placed in their medical record.

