The following testing is performed at the University of Minnesota.

**Blood Immune Cell Analyses** - Flow and/or mass cytometry analysis of blood cells may be conducted to detect surface markers that define immune cell and lymphocyte subsets (such as NK, NKT, B, and T cells, both CD4 and CD8), as well as intracellular markers that define additional parameters (such as regulatory T

cells (Foxp3) and proliferating cells (Ki67)). RNA sequence analysis may also be conducted to assess the gene expression profile in immune cells.

Quality of Life Assessments Exploratory Research Assessments will be performed on various quality of life parameters. Assessments are completed by the participant or, through oral response to a member of the research team administering the assessment. The Functional Assessment of Cancer Therapy - General (FACT-G) is a validated 27-item questionnaire designed to measure four domains of health related quality of life in cancer patients: physical, social, emotional, and functional well-being using a 5 point Likert-type score based on patient recall of the last 7 days.

**The Skin Condition Questionnaire** is a 3 question binary (Y/N) survey created by HCW Biologics asking about skin changes at the injection site and overall changes in the skin noted by the participant. For yes responses, the participant is asked to describe the changes.

**Tumor Biopsies (Optional)** Patients will be approached based on safety and feasibility of accessible tumor tissue. A separate research biopsy consent is required. Biopsy samples will be stored for future research studies. Immunohistochemistry analysis and genomic, transcriptomic and proteomic molecular profiling may be performed on fresh/frozen and/or formalin-fixed, paraffin embedded (FFPE) tumor tissue. All such analyses will be retrospective and exploratory. Biopsies will be performed according to the institution's standard procedures. Tumors used for biopsy should not be lesions used as RECIST target lesions unless there are no other lesions suitable for biopsy.

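### The only pre-dose FACT-G may be completed while a patient is on, or recalling, prior anti-cancer therapy, so later comparisons with it may be confounded; a pre-dose form on Cycle 1 Day 1 would largely avoid this

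*Combined protocol and SAP*

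**What the plan says.** - **Schedule.** The Section 8.2 table marks the FACT-G at Baseline/Screening, every 4 cycles (12 weeks) and at End of Treatment. Cycle 1 Day 1 is not marked, and no footnote narrows the timing.
- **Screening window.** The Section 8.1 table heads this column "Within 28 days of Cycle 1 Day 1 unless o/w noted" and shows Day -28 to Day -1, with no Day 0. The Section 8.2 table does not repeat the limit, but its footnote 10 says "Biopsy collection is exempt from the 28 day limit". That exemption makes sense only if the limit governs the other items in the table.
- **Washout.** Section 4.2.5 excludes surgery, radiotherapy, chemotherapy, other immunotherapy or "investigational therapy within 14 days before treatment start".
- **Recovery.** Section 4.1.3 requires "Resolved acute effects of any prior therapy to baseline or Grade ≤1 NCI CTCAE v5", apart from effects the enrolling investigator judges not to be a safety risk. It does not mention the FACT-G date.
- **Recall.** Section 8.2 describes the FACT-G as scored "based on patient recall of the last 7 days". Appendix V includes the item "I am bothered by side effects of treatment".
- **Role.** Section 1.3 lists evaluation of the effect on quality of life among the correlative objectives, and Section 8.2 calls these assessments exploratory. Section 13.2 names no FACT-G analysis.

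**The concern.** The trial has no control arm. If the quality-of-life objective is to say anything about an effect, the natural comparison is each patient's later FACT-G against the baseline form. A patient who stops early may have only two forms, baseline and End of Treatment, so the baseline is half of that patient's evidence.

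Every participant has failed at least two prior lines. A form completed early in screening can describe a week on, or just after, the previous treatment. The physical items (energy, nausea, pain, side effects, feeling ill, time in bed) would then partly reflect that treatment. If those effects fade before dosing, the later form looks better for reasons unrelated to HCW9218. If the disease worsens between an early form and the first dose, the later form looks worse for reasons equally unrelated to it.

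Other baselines are better protected. Section 8.1 footnote 1 accepts imaging up to 42 days old only "in the absence of intervening anti-cancer therapy", and it requires eligibility labs within 14 days of treatment start. Dosing weight is taken on Cycle 1 Day 1 or within 14 days before. The baseline PK and correlative-marker samples are drawn within 24 hours before the dose. The FACT-G has no comparable rule.

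**Working it through.** The plan states no sample size, power or effect size for the FACT-G, so there is no figure to reproduce. The check is a count of calendar days.

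**Inputs**
- Permitted form days d: Day -28 to Day -1, which is 28 days (Section 8.1).
- Last day L on which prior therapy is allowed: Day -15 if the fourteenth day before dosing is itself barred, Day -14 if it is not (Section 4.2.5 can be read either way).
- Recall: 7 days (Section 8.2, Appendix V). The earliest day recalled is d - 6 if the day of completion counts, or d - 7 if it does not.

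**Form completed while therapy is still allowed (d ≤ L)**
- L = -15: Day -28 to Day -15, 14 of 28 days.
- L = -14: Day -28 to Day -14, 15 of 28 days.

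**Form whose recall can reach a day on therapy (earliest day recalled ≤ L)**

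| Last therapy day | Recall starts at | Latest affected form day | Days affected |
|---|---|---|---|
| -15 | d - 6 | -9 | 20 of 28 |
| -15 | d - 7 | -8 | 21 of 28 |
| -14 | d - 6 | -8 | 21 of 28 |
| -14 | d - 7 | -7 | 22 of 28 |

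Only the last 6 to 8 days of the window (28 - 22 to 28 - 20) guarantee a recall period free of prior therapy.

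**A pre-dose form on Cycle 1 Day 1.** There is no Day 0, so the 7 days before Day 1 are Day -7 to Day -1. All are later than Day -14, so the recall lies inside the washout under every reading above.

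**Gap to the next form.** A 12-week form taken 84 days after Cycle 1 Day 1 falls 84 + 1 = 85 to 84 + 28 = 112 days after a screening form. An End of Treatment form can come sooner.

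**Scale.** The FACT-G maximum is 27 × 4 = 108 points, and physical well-being is 7 × 4 = 28 of these. The side-effects item can contribute at most 4 of 108 (3.7%). The documents give no FACT-G means or standard deviations, so the count shows exposure to the problem and not the size of a bias.

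**The case against.** The strongest reply is that nothing in the plan depends on this comparison. Section 13.2 specifies no FACT-G change score and no attribution to drug, only general descriptive statistics and plots, and the measure is exploratory in at most 24 patients spread over several dose levels. This stands. A reader might infer that the plan itself credits recovery from earlier treatment to HCW9218, but the documents do not support that. The risk lies in how a later descriptive comparison is read.

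Second, the problem is conditional. It needs a patient treated within roughly five weeks of dosing and a form completed early. Section 4.1.3 also limits residual toxicity by entry. This stands in part: the criterion has an investigator exception and is not tied to the form, so a patient could complete the FACT-G while symptomatic, recover and then qualify. Nothing shows how often that would happen.

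Third, a reader might infer a bias toward benefit. The documents do not fix the sign, since fading treatment effects and worsening disease pull in opposite directions. By 12 weeks, disease course and selection of patients still on treatment also affect the comparison, and no choice of baseline day removes them.

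Finally, the side-effects item is standard wording from a validated instrument. It illustrates the ambiguity but is not itself a defect. The evidence is in the schedule, the washout and the recall period.

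**Conclusion.** The timing weakness holds; the stronger consequences do not. On about 20 to 22 of the 28 permitted days the only pre-dose FACT-G could cover days on prior therapy, and no rule prevents it. A comparison of the 12-week or End of Treatment scores with that baseline may therefore confound recovery from earlier treatment, or disease drift before dosing, with an effect of HCW9218.

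The count takes the 28-day limit to apply to the Section 8.2 table, as footnote 10 implies, and prior therapy to end on the latest permitted day. It is a count of permitted days. Reading it as about three-quarters of patients affected would be wrong, because the documents do not say when patients complete the form or when they last had treatment. No bias in points can be given either. A 1-point shift in each of the 7 physical items would be 7 points, for example, but that shift would be pure assumption.

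Severity is low. The MTD, DLT rules, dose assignment, sample size and secondary endpoints are untouched. The point is worth acting on because the change is nearly free and a poorly timed baseline cannot be collected again.

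**What to change.** In the Section 8.2 table, move the FACT-G baseline mark from Baseline/Screening to Cycle 1 Day 1 and label it as completed before the dose, as is already done for several research blood samples. State that this form is the baseline for any FACT-G comparison.

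For patients already enrolled with only a screening form, report the form date and the date of last prior therapy alongside the scores, and describe change without attributing it to HCW9218.

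The cost is one table cell and a sentence. Cycle 1 Day 1 is already a clinic visit and the form replaces the screening one, so no visit or questionnaire is added. There are two downsides: a short form joins the Day 1 pre-dose tasks, and baselines before and after the amendment differ in timing, so they should be identified separately in any listing or plot. The change reduces the problem without removing it entirely, because recovery from earlier treatment can continue beyond a 14-day washout.

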## FACT-G (Version 4)

Please circle or mark one number per line to indicate your response as it applies to the past 7 days.

	EMOTIONAL WELL-BEING	Not at all	A little bit	Some- what	Quite a bit	Very much
GE1	I feel sad	0	1	2	3	4
GE2	I am satisfied with how I am coping with my illness	0	1	2	3	4
GE3	I am losing hope in the fight against my illness	0	1	2	3	4
GE4	I feel nervous	0	1	2	3	4
GE5	I worry about dying	0	1	2	3	4
GE6	I worry that my condition will get worse	0	1	2	3	4
	FUNCTIONAL WELL-BEING	Not at all	A little bit	Some- what	Quite a bit	Very much
GF1		at all	bit	what	a bit	much
	I am able to work (include work at home)	at all	bit 1	what	a bit	much
GF1	I am able to work (include work at home)	0 0	bit 1 1	what 2 2	a bit 3 3	much 4 4
	I am able to work (include work at home)	0 0	bit 1	what	a bit	much
GF2	I am able to work (include work at home)	0 0 0	bit 1 1	what 2 2	a bit 3 3	much 4 4
GF2 GF3	I am able to work (include work at home)	0 0 0 0	bit 1 1 1	what 2 2 2	3 3 3	4 4 4
GF2 GF3 GF4	I am able to work (include work at home)	0 0 0 0 0 0 0 0	bit 1 1 1 1	2 2 2 2	3 3 3 3 3	4 4 4 4

English (Universal)
Copyright 1987, 1997
16 November 20
Page 2 c

